## **5.3 Surgery**

### *5.3.1. treatment for the primary*

Whenever 12 weeks after radiotherapy clinical tumor residue is present on the vulva, a local resection of that area with a clinical tumorfree resection margin of at least 1 cm must be performed. It is to be preferred, depending on the size of the defect to close this with a well vascularized flap.

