### **5. Treatment schedule, expected toxicities, dose modifications**

The general treatment principle is that definitive radiochemotherapy is the main treatment for the locally advanced vulvar disease. Surgery for the primary vulvar tumor will only be performed in case of:

1. progressive disease
2. the presence of histologically proven residual disease 12 weeks after the last course of radiochemotherapy treatment.

Patients will only undergo a groin lymph node dissection when the nodes are pathologically positive, bulky on clinical examination or bulky on imaging studies.

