### *5.3.2 treatment for the regional lymph nodes*

Patients with cN0 groin lymph nodes and no enlarged/suspicious lymph nodes on imaging (ultrasound/CT/MRI) will be treated with radiochemotherapy only. Patients with cN1/2 groin lymph nodes are treated with either a nodal debulking upfront or a bilateral inguino-femoral lymph node dissection 8-12 weeks after the radiotherapy. It is recommended, in case of residual vulvar disease, to combine local and regional surgical treatment.

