## **6.3 During first follow-up after radiotherapy at 4 and 8 weeks and response assessment at 12 weeks.**

The patient will be seen 4 and 8 weeks after the end of the radiochemotherapy by the radiation oncologist and gynaecologist and physical and gynaecological examination will be performed. At that time short term morbidity must be assessed and progression of disease must be ruled out. At 12 weeks after the end of the radiochemotherapy response assessment will be done by the radiation oncologist and gynaecologist. Special attention is to be given to the vulva and groin area by visual examination and palpation in search of residual disease. Lesions suspicious for recurrence are to be biopsied. Response will be reported according to RECIST criteria (addendum 2, page 23).

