## 6.6 Summary Table

Required investigations	Prestudy	After initial surgery*	During radiochemotherapy	After radiochemotherapy	After secondary surgery**	During follow up
						yr. 1-2: 3-monthly yr 2-5: 6-monthly
Day	-28 tot 0	-28 tot 0	Start day 0  weekly	4, 8 and 12 weeks after last radiochemotherapy	> 12 weeks after last radiochemotherapy	
History	X 1					
Phys/gyn exam	X 1/ 2			X 1/2		X 1/2
WHO	X 1		X 2/ 3	X 2		
TNM	X 1					
Photo	X 1			X 2		
Chest X-ray	X 1					
CT/MRI/US	X 1			X 1/2 ***		
Haematology	X 1		X 2/ 3	X 1		
Biochemistry	X 1		X 2/ 3	X 1		
Path lymph nodes		X 1			X 1	
Path primary tumor	X 1				X 1	
Short-term morb		X 1	X 2/ 3	X 2	X 1	
Long term morb						X 1/2

\* Only when upfront surgery is performed for clinically (and pathologically confirmed) positive groin lymph node metastases

\*\* Only when salvage surgery for the primary or groin dissection is performed

\*\*\* Optional

- 1) gynecologic oncologist
- 2) radiation oncologist
- 3) medical oncologist

 Haematology: Hb, Ht, platelets, leucocytes  
Chemistry: Na, K, Creatinin, ureum, Bilirubin, gGT, AF, ASAT, ALAT, LDH.  
Creatinin clearance if plasma creatinin > 100 umol/l.

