### **7.1 Assessment of locoregional tumor response**

Twelve weeks after the full course of radiochemotherapy the patient will be assessed by the radiation oncologist and gynecologic oncologist. A photograph of the tumor with an adjacent ruler must be taken. The residual primary tumor will be measured in two directions and the longest diameter is assessed according to the RECIST criteria (see addendum 2). In case a clinical complete response is confirmed the groins will be treated as described in section 5.3 whenever no upfront debulking was performed. A complete response of the groin lymph nodes is defined as no residual disease in the groins after radiochemotherapy and surgery. No further surgery for the vulvar area is considered. Only when there is doubt about the clinical complete response or no agreement between gynecologist and radiation oncologist can be achieved, a mapping procedure must be performed to confirm the complete response also pathologically. In all other cases salvage surgery must be considered and if necessary reconstructive surgery or exenterative surgery with stoma formation must be considered.

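### Section 5 limits surgery of the vulvar primary to progression or histologically proven residue, but 5.3.1 mandates resection of clinical residue with no histology condition

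*Protocol*

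**What the plan says.** Section 5 opens with the general treatment principle. It states that "Surgery for the primary vulvar tumor will only be performed in case of" two situations: progressive disease, or "the presence of histologically proven residual disease 12 weeks after the last course of radiochemotherapy treatment".

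Section 5.3.1 then says: "Whenever 12 weeks after radiotherapy clinical tumor residue is present on the vulva, a local resection of that area" must be performed, with a clinically tumour-free margin of at least 1 cm. Depending on the size of the defect, the preference is to "close this with a well vascularized flap". Histology is not mentioned.

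Three other places touch the same decision:

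- Section 5.3.2: "It is recommended, in case of residual vulvar disease, to combine local and regional surgical treatment". Histology is again not mentioned.
- Section 6.3, which covers the 12-week response assessment: "Lesions suspicious for recurrence are to be biopsied". It does not say what follows from the result.
- Section 7.1: if the clinical complete response is in doubt, or the two assessors disagree, "a mapping procedure must be performed to confirm the complete response also pathologically". In all other cases short of a complete response, salvage surgery must be considered.

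**The concern.** Two operative instructions use different triggers for the same operation. Section 5 is restrictive (only these grounds, histology required). Section 5.3.1 is mandatory (whenever, must) and rests on clinical appearance alone. A centre that follows 5.3.1 to the letter would excise a lesion that biopsy has shown to be free of tumour, in a fully irradiated vulva and possibly with a flap.

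Section 5 excludes that operation. The trial also wants to avoid it, since Section 1.6 aims at local control that makes local salvage surgery unnecessary. Section 1.3 reports that surgery in a previously irradiated area can bring significant wound healing problems and treatment-related mortality.

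Morbidity and reconstructive surgery are secondary endpoints in Section 2.3. If centres in this multicentre trial apply different sections, those endpoints would partly record which section was applied.

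**Working it through.** No arithmetic applies: the point depends on no sample size, error rate or response rate. The check is to run each possible 12-week finding through both rules.

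| Finding at 12 weeks | Section 5 | Section 5.3.1 | Result |
|---|---|---|---|
| Progression | Surgery allowed, no histology needed | Resection required if clinical residue is present | Compatible |
| Clinical residue, histology positive, no progression | Surgery allowed | Resection required | Compatible |
| Clinical residue, histology negative, no progression | Surgery excluded | Resection required | Contradiction |
| No clinical residue | Surgery only on one of the two grounds | Not triggered | Compatible |

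Only the third row conflicts. The next step is to ask whether another section decides that row.

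1. Section 6.3 supplies a biopsy at the right visit. Its preceding sentence directs the search for residual disease in vulva and groin. It does not tie the decision to operate to the biopsy result.
2. Section 7.1 offers mapping when a clinical complete response is doubtful or disputed. A persisting lesion with a negative biopsy might be classed as doubtful, but the text does not say so. If it is not so classed, the fallback is that surgery must be considered. This wording is weaker than the obligation in 5.3.1 and looser than the restriction in Section 5, so it is a third formulation and does not settle the matter.
3. Section 5.3.2 refers to residual vulvar disease without saying whether clinical or proven residue is meant.
4. No section gives either rule precedence in so many words.

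The third row therefore remains open.

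The last step is to ask which results could be affected. Sections 2.3 and 7.1 fix the vulvar response at the 12-week assessment by examination, with mapping in case of doubt. Salvage surgery of the primary comes after that assessment, and nothing makes the response score depend on whether the patient is then operated on. What changes is who is operated on, and with it surgical morbidity and the record of reconstructive surgery.

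**The case against.** The strongest defence reads the sections as a whole. Section 5 is the stated principle and decides who is operated on, 6.3 provides the biopsy, and 5.3.1, a subsection of Section 5, mainly says how to operate (local resection, margin, closure). On that reading there is no conflict for proven residue, and a doubtful lesion has a route through mapping in 7.1.

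Much of this stands. It is probably what the authors meant, and it confines the problem to one group of patients. It does not remove the problem, because 5.3.1 states its own trigger and makes it compulsory, so it is more than a note on technique.

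A reader might also infer that the histology needed before surgery is never scheduled, because the row "Path primary tumor" in the 6.6 table has no mark at 4, 8 and 12 weeks. The protocol does not support this. Section 6.3 calls for the biopsy at that visit, and the table leaves out other conditional sampling as well. Section 6.1 requires fine-needle aspiration of suspicious nodes before treatment, and 6.5 requires biopsy of suspicious lesions during follow-up, yet neither has a pathology mark in its column. The missing mark reflects how the table is built.

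**Conclusion.** The contradiction is real and stands in the current text. It is confined to patients with clinical vulvar residue at 12 weeks, negative histology and no progression. For them one rule forbids the operation and the other requires it. The consequence is possible resection of tumour-free irradiated tissue, and morbidity and reconstructive-surgery results that may depend on which section was followed.

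The size cannot be stated. The protocol gives no share of clinical vulvar residue that proves tumour-free. A reader might take the series in Section 1.4, where some operated patients had a pathological complete response, as an estimate. That series concerned inoperable groin disease and says nothing about vulvar lesions that remain clinically visible.

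A reader might also infer a bias in the response rate or in the two-stage decision rule. The protocol does not support that either, because the vulvar response is scored at the 12-week assessment and not from the later decision to operate.

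The conclusion rests on a literal reading of the two rules. That centres would in fact diverge is a possibility, not something the protocol shows. The correction is still worth making, because the instruction as written can send a patient to an operation that the protocol's own principle excludes.

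**What to change.** Bring the subsections into line with the principle in Section 5:

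- 5.3.1: *Whenever histologically proven tumor residue is present on the vulva 12 weeks after radiochemotherapy, a local resection … must be performed*, with margin and closure as now.
- 5.3.2: *in case of histologically proven residual vulvar disease*.
- 6.3: *Lesions suspicious for residual or recurrent disease are to be biopsied; in the absence of progression, residue is resected only if histologically proven.*

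The qualifier about progression matters, because the progression ground in Section 5 carries no histology condition and should stay unchanged. The 6.6 table needs no change. Nor is a new rule needed that sends every biopsy-negative lesion to mapping: 7.1 already provides mapping where there is doubt, and going further would be a clinical choice for the investigators.

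The cost is wording in three sections. No histology is added beyond what Section 5 and 6.3 already call for, and no endpoint definition, sample size or analysis changes.

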### *5.3.2 treatment for the regional lymph nodes*

Patients with cN0 groin lymph nodes and no enlarged/suspicious lymph nodes on imaging (ultrasound/CT/MRI) will be treated with radiochemotherapy only. Patients with cN1/2 groin lymph nodes are treated with either a nodal debulking upfront or a bilateral inguino-femoral lymph node dissection 8-12 weeks after the radiotherapy. It is recommended, in case of residual vulvar disease, to combine local and regional surgical treatment.

## **5.4 Toxicity**

### *5.4.1 Radiotherapy:*

Short term side effects are skin desquamation in the majority of patients and diarrhoea, nausea and spasmodic abdominal pain. Late effects are a mild form of lymph edema, skin fibrosis and a higher risk on femoral neck fractures.

### *5.4.2 Chemotherapy:*

Most side effects are on the short term and constitute of vomiting, bone marrow depression, diarrhea, mild alopecia, and hand-foot syndrome.

## **5.5 Treatment duration**

Treatment duration is until all radiotherapy has been administered. In case for some reason (eg progression under radiotherapy) it is decided to discontinue protocol treatment, this should be clearly explained and specified on the treatment forms stating the reason and the treatment applied. Patients will be evaluated according to the intention to treat analysis.

Patients may also discontinue protocol therapy in the following instances:

1. Intercurrent illness which would, in the judgment of the investigator, affect patient safety, the ability to deliver treatment or the primary study endpoints
2. Request by patient.
3. Unacceptable toxicity.
4. At time of progression of disease outside the loco regional area.
5. Patients will have follow-up at least up to two years after study entry, and every six months thereafter, preferably until death. (see 6.5)

## **5.6 Concomitant therapy**

Other anti-cancer treatment or investigational therapy while patient is enrolled in the protocol treatment is prohibited. A different radiotherapeutic regimen other than specified by the protocol is prohibited. Medication for other disease is allowed, but generic name and dose have to be stated on the on-study form, or on the treatment forms.

Medication for pain-relief, anti-emetic medication or other supportive medication is permitted.

## **6 Clinical evaluation, laboratory tests, follow-up**

Patients can be registered for this study if they have pathologically proven squamous cell cancer of the vulva amenable for curative treatment but not curable with surgery unless extensive reconstructive surgery or a colostomy or urostomy is performed. Protocol treatment should start within 4 weeks of registration.

### **6.1 Before treatment start**

The following examinations should be performed within 4 weeks prior to treatment:

- Medical history
- Physical and gynecological examination
- WHO performance status
- TNM stage

- A photograph of the tumor with an adjacent ruler must be taken.
- Pathology of the primary tumor.
- The primary tumor must be localized exactly, measured in two dimensions and the margins towards the vagina, urethra, anus and clitoris must be stated in mm.
- The clinical description of the groin nodes must include: number of palpable nodes, side of nodes, size, mobility and whether or not a lymphangitis is present.
- CT, MRI or US scan of the groin region (If CT/MRI/US scan shows a suspicious lymph node or in case of clinical suspicion, FNA should be performed).
- Chest X-ray
- Routine blood tests (leukocytes, platelets, Hb, HT)
- Serum creatinine, ASAT, ALAT, bilirubin and alkaline phosphatase
- Socio-demographic data

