# Flowsheet

## Phase II study of definitive radiochemotherapy for locally advanced squamous cell cancer of the vulva: an efficacy study

# **1. Background and introduction**

## **1.1 General introduction**

Cancer of the vulva is a relatively rare disease with an annual incidence of 2-3 per 100.000 women. The main histological subtype is squamous cell cancer (75%) followed by basal cell cancer (15%) and other types like adenocarcinoma, melanoma and sarcoma's in 10% of cases [1]. In the Netherlands each year 150-200 new patients are diagnosed with vulvar cancer [2]. A steep rise in age specific incidence rate is seen above 65 years with the majority of patients being 75 years or older. About 70% of patients with squamous cell cancer (SCC) of the vulva present with a local tumor confined to the vulva (cT1/T2). These patients are usually treated with a radical local excision and uni- or bilateral inguinal femoral lymph node dissection [3]. When lymph nodes are negative (70-80% of patients), survival is high with a 5 year disease specific survival of 80-90%. When the groin nodes are positive survival decreases from 30% in case extra capsular tumor is found, till 60% in case the lymph node metastases are intracapsular [4].

In 30% of the patients tumors are classified as T3/T4 tumors with either extension of the tumor to the vagina, the proximal urethra or anus (cT3) or extension to the upper urethra or bladder, upper anal canal or rectum or the tumor is fixed to the pubic bone (cT4). Those cases in which the typical radical surgical excision of the vulva will not remove the cancer with adequate margins are considered to be locally advanced or cT3/T4 vulva carcinoma. The primary tumor causes serious local problems such as pain while sitting, discharge, bleeding from necrotic tumor and a foul odor. Positive lymph nodes are found in 50%-60% of patients with T3/T4 tumors. Frequently these nodes are ulcerating and or fixed to the femoral vessels in the groin. These patients presenting with locally advanced disease (cT3/T4) pose a specific problem regarding the treatment.

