### **2.2 secondary objectives**

The secondary objective would be to determine short-term morbidity defined as desquamation of the skin, infection, long-term morbidity defined as edema, fibrosis, the incidence of fecal and or urinary continence, and or incidence of reconstructive surgery performed and treatment related mortality. Longterm morbidity and the rate of locoregional recurrences will be evaluated at 24 months after the end of radiochemotherapy.

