### **7.4 Assessment of locoregional recurrence 24 months after registration**

Two years after the full course of radiochemotherapy the patient will be assessed by the radiation oncologist and gynecologic oncologist. A photograph of the local situation at the vulva area with an adjacent ruler must be taken. Measurements should be done according to RECIST criteria (Addendum 2). Whether or not reconstructive surgery or exenterative surgery with stoma formation has been performed should be mentioned. Morbidity should be described such as lymphedema, fibrosis, and continence (both urinary and fecal).

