### Safety Monitoring

Adverse events will be monitored on an ongoing basis and their frequencies reported semi-annually. Toxic effects will be categorized using the NCI Common Terminology Criteria for Adverse Events, Version 3.0. The worst event for each patient will be described. Both events related and unrelated to treatment will be captured.

Clinical and laboratory data will be tabulated and compared to normal ranges for the institution.

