### RTOG/EORTC Late Radiation Morbidity Scoring Scheme

Use for toxicity occurring greater than 90 days after radiation therapy.

Grade									
Toxicity		0	1	2	3	4			
Bladder-Late RT Scoring	Morbidity	No change from baseline	Slight epithelial atrophy/minor telangiectasia (microscopic hematuria)	Moderate frequency/generalized telangiectasia/intermittent macroscopic hematuria	Severe frequency and dysuria/severe telangiectasia (often with petechiae); frequent hematuria; reduction in bladder capacity (< 150 cc)	Necrosis/contracted bladder (capacity < 100 cc)/severe hemorrhagic cystitis			
Bone-Late RT Scoring	Morbidity	No change from baseline	Asymptomatic; no growth retardation; reduced bone density	Moderate pain or tenderness; growth retardation; irregular bone sclerosis	Severe pain or tenderness; complete arrest of bone growth; dense bone sclerosis	Necrosis/spontaneous fracture			
Brain-Late RT Scoring	Morbidity	No change from baseline	Mild headache; slight lethargy	Moderate headache; great lethargy	Severe headaches; severe CNS dysfunction (partial loss of power or dyskinesia)	Seizures or paralysis; coma			
Esophagus-Late RT Scoring	Morbidity	No change from baseline	Mild fibrosis; slight difficulty in swallowing solids; no pain on swallowing	Unable to take solid food normally; swallowing semi-solid food; dilatation may be indicated	Severe fibrosis; able to swallow only liquids; may have pain on swallowing; dilation required	Necrosis/perforation; fistula			
Heart-Late RT Scoring	Morbidity	No change from baseline	Asymptomatic or mild symptoms; transient T wave inversion and ST changes; sinus tachycardia > 110 (at rest)	Moderate angina on effort; mild pericarditis; normal heart size; persistent abnormal T wave and ST changes; low QRS	Severe angina; pericardial effusion; constrictive pericarditis; moderate heart failure; cardiac enlargement; EKG abnormalities	Tamponade/severe heart failure/severe constrictive pericarditis			
Joint-Late RT Scoring	Morbidity	No change from baseline	Mild joint stiffness; slight limitation of movement	Moderate stiffness; intermittent or moderate joint pain; moderate limitation of movement	Severe joint stiffness; pain with severe limitation of movement	Necrosis/complete fixation			

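### No pre-treatment grading of morbidity or continence is scheduled, so symptoms present at entry cannot be reliably separated from late treatment morbidity or loss of function

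*Protocol*

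**What the plan says.** **Before treatment.** Section 6.1 states "The following examinations should be performed within 4 weeks prior to treatment". It then lists history, examination, WHO status, TNM, a photograph, pathology, tumour and node description, imaging, chest X-ray, blood tests and socio-demographic data. The item closest to function is anatomical: "the margins towards the vagina, urethra, anus and clitoris must be stated in mm". No symptom is graded, and continence, an existing stoma and leg edema are not listed.

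**Schedule table.** In Table 6.6 the row labelled "Short-term morb" and the long-term morbidity row both have an empty Prestudy cell. The short-term row is marked after initial surgery (only for patients with upfront groin surgery), during and after radiochemotherapy, and after secondary surgery. The long-term row is marked only in follow-up.

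**What is reported later.** Section 2.2 names "long-term morbidity defined as edema, fibrosis, the incidence of fecal and or urinary continence". For the two-year assessment, section 7.4 says "Morbidity should be described such as lymphedema, fibrosis, and continence (both urinary and fecal". Section 7.3 sends all long-term morbidity to the RTOG/EORTC scheme in Addendum 3, where grade 0 in each named organ row is "No change from baseline". Safety Monitoring in section 8 adds: "The worst event for each patient will be described. Both events related and unrelated to treatment will be captured".

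**State at entry.** Section 1.1 says the tumours may extend to the urethra, bladder, anus or rectum, that groin nodes are frequently ulcerating or fixed, and that the primary causes "pain while sitting, discharge, bleeding from necrotic tumor and a foul odor".

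**The concern.** The protocol adopts outcome definitions that need a known starting state but schedules no structured record of that state. Whether morbidity developed after treatment, and whether an organ is unchanged from baseline, can be decided only against something recorded beforehand.

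This matters more here than in many trials. The disease sits in the organs whose function is being judged, and its symptoms overlap with the items scored later. There is one arm, so no control group shows how much of a late symptom rate belongs to the tumour. The error can run in two directions. A symptom carried over from entry can be read as treatment morbidity, and a patient who regains continence after a response looks the same as one who never lost it. Avoiding extensive surgery and stomas is the rationale of the study, so function is among its more important secondary results.

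An analysis plan cannot repair this, because it cannot create a baseline that was not collected.

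**Working it through.** The protocol states no figure on this point, so none can be reproduced. The check sets the sections against each other and then illustrates direction and range.

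**1. Is there a baseline?** Section 6.1 has no graded symptom and no functional item. Table 6.6 agrees: both morbidity rows are empty under Prestudy. The after-initial-surgery column (day -28 to 0) covers only patients with upfront groin surgery, and morbidity recorded after that operation is not a baseline of tumour symptoms. For all other patients, CTCAE grading first appears in section 6.2, during radiochemotherapy.

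**2. Do the later definitions need one?** Yes, in three places:
- Section 7.3 counts morbidity that arose after radiochemotherapy or discharge. It sets no relatedness condition.
- Addendum 3 defines grade 0 by reference to baseline for each named organ. Grades 1 to 4 are mostly absolute descriptions, so an unchanged entry symptom can meet them. Examples are rectal discharge or bleeding (intestine grades 1 to 2), hematuria (bladder grades 1 to 3) and ulceration (skin and mucous membrane grade 4).
- Continence (sections 2.2, 2.3 and 7.4) has no row in Addendum 3 and no entry value elsewhere.

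**3. Are entry symptoms plausible on the protocol's own account?** Pain, discharge and bleeding are stated in section 1.1. Involvement of the urethra, bladder, anus or rectum is also stated, but that is anatomy. How many patients are incontinent or have leg edema at entry is not stated.

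**4. Direction and range (illustration only).** Let t be true treatment morbidity, b the share with the symptom at entry, and k the share of those whose symptom is still present at assessment and is recorded as morbidity. If entry symptoms and treatment morbidity are independent:

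apparent rate = t + (1 − t) × b × k

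All three inputs are assumed. With t = 0.20:
- k = 0.5: b = 0.10 gives 0.20 + 0.80 × 0.10 × 0.5 = 0.24; b = 0.30 gives 0.32; b = 0.50 gives 0.40.
- k = 1: b = 0.10 gives 0.28; b = 0.30 gives 0.44; b = 0.50 gives 0.60.
- k = 0 (all symptoms resolve or are correctly screened out by history): the rate stays at 0.20.

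The excess (1 − t) × b × k thus runs from 0 to 40 percentage points over these assumptions. If all 68 planned patients were assessable, the half-persisting excesses of 4, 12 and 20 points would be 0.04 × 68 = 2.7, 0.12 × 68 = 8.2 and 0.20 × 68 = 13.6 patients. The formula covers upward bias only. Regained function is a separate loss of information that it does not measure.

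**The case against.** A reader might infer that tumour symptoms *will* be counted as treatment toxicity, or that the two-year incontinence rate will be inflated by some definite amount such as 10 to 30 points. The documents do not support either reading, and the case against them is substantial:

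- **Definitions.** Section 7.2 limits short-term morbidity to treatment-related events, section 7.3 limits long-term morbidity to what developed afterwards, and section 12.1 defines an adverse event as following treatment. Pre-existing conditions are nominally excluded. This stands, but the exclusion rests on an ungraded history and examination.
- **Safety summary.** Capturing related and unrelated events suggests that relatedness will be recorded. It does not say that unrelated events are reported as toxicity. This stands.
- **Day 0.** The on-treatment column of Table 6.6 starts at day 0, so CTCAE grading of skin, bowel and urinary symptoms may begin on the first treatment day. This is a partial mitigation. The table does not require grading before the first dose, and it does not set a continence assessment.
- **Addendum 3.** There is no row for continence or lymphedema, so the baseline-referenced grade 0 does not govern those two. The catch-all row has grade 0 as none. Where the wording does apply, it tells the assessor to score an unchanged condition as 0, which works against the bias. Both points are correct, but that instruction can be followed only if the earlier condition is known.
- **Entry symptoms.** Incontinence and leg edema at presentation are nowhere documented, and active uncontrolled infection is excluded by section 3.1. This stands. It limits what can be said about size.
- **Forms.** An on-study form is mentioned in section 5.6 and the CRFs are still to be developed (section 11.1), so symptoms might be captured there. That is possible, but nothing in the protocol requires it.
- **Discrete events.** Stoma formation, reconstructive surgery and treatment-related death are events that need no graded baseline. This stands.

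**Conclusion.** The gap is real and confined to secondary outcomes. Sections 6.1 and 6.6 provide no graded morbidity and no continence status before treatment, while section 7.3, Addendum 3 and the continence endpoint all presuppose a known starting state. Symptoms present at entry *can* be counted as late morbidity or loss of function and cannot be reliably separated from treatment effect in one arm. Continence regained after response cannot be shown.

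The size is unknown. The illustrated rates rest on assumed values of true morbidity, entry prevalence and persistence, on independence between entry symptoms and treatment morbidity, and on an error rate in applying the exclusions that nobody can state in advance. Only the direction is firm: upward whenever an entry symptom persists and is not recognised as pre-existing. The primary endpoint, the two-stage rule and the sample size are untouched. This is a change that should be made, not one on which the trial's main conclusion depends.

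**What to change.** Add a baseline morbidity item to section 6.1 and a corresponding entry in the Prestudy column of Table 6.6, covering:

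- pain, bleeding, bowel symptoms, urinary symptoms and skin condition including ulceration, graded on the scales used later;
- urinary continence, fecal continence, stoma present, and leg edema, as yes/no or a simple grade, because Addendum 3 has no row for continence or lymphedema. The same items should be used at follow-up.

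Report late morbidity and continence as new or worsened relative to baseline, beside the raw worst grade, and show continence regained as well as lost.

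The cost is one extra CRF page, completed at a visit where history and gynaecological examination are already required. No visit, test or treatment is added. For patients already enrolled, the values would have to be taken from their charts. They will be less complete and should be flagged as retrospective.
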